5.15. Summary of Analyses of Other Efficacy and Exploratory Endpoints

Endpoint	Analysis Method
Analysis at all time points in the proportion of participants free of panic attacks as assessed by participant daily diary	Repeated measure logistic regression described in Section 5.11.2
Change from baseline at all time points in the PDSS total score and subscores	MMRM model described in Section 5.12.1.2
Change from baseline at all time points in panic attack frequency	Same methods described in Section 5.12.2.2
Change from baseline in the CGI-S score at all time points	MMRM model described in Section 5.12.1.2
Change from baseline in the HAM-A total score at all time points	MMRM model described in Section 5.12.1.2
Change from baseline in the EQ 5D-5L at all time points	MMRM model described in Section 5.12.1.2
Change from baseline in the SDS total score at all time points	MMRM model described in Section 5.12.1.2

5.16. Interim Analysis

The trial is designed to be conducted to full completion without interim analyses. If any interim analysis becomes necessary, all plans will be prespecified prior to the conduct of such analyses.

5.17. Safety Analyses

All safety analyses will be performed on the Safety Analysis Set. Should any participants receive a treatment other than their randomized treatment, the treatment as received will be used in the safety presentation.

5.17.1. Adverse Events

Adverse events will be mapped to the most current MedDRA version preferred term and system organ class. If a participant experiences multiple events that map to a single preferred term, the greatest severity and strongest investigator assessment of relation to IMP will be assigned to the preferred term for the appropriate summaries. Events with missing severity or relationship will be classified as outlined in [Section 3.2](#). Summaries of treatment-emergent AEs will include any AEs reported beginning with the initiation of study drug on Day 1 through last follow-up. The occurrence of TEAEs will be summarized by treatment group using preferred terms, system organ classes, and severity. Separate summaries of treatment-emergent serious adverse events (TESAEs), TEAEs related to IMP, AESIs (including AEs related to abuse potential and AEs involving medication handling irregularities), events leading to the discontinuation of IMP, and events leading to the discontinuation of study will be generated respectively.

Presentations of AEs by onset titration versus maintenance period will be prepared.

All adverse events will be included in the listings.

Missing onset dates will be imputed as previously outlined in [Section 4.1.19](#).

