## **6.5. Dose Modification**

No dose modifications are permitted during the trial.

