#### **9.3.5. Safety Analyses**

Treatment-emergent adverse events (serious and nonserious) will be coded according to MedDRA and summarized by treatment group, system organ class, and preferred term. Further summaries will be done by severity (assessed by National Cancer Institute-Common Terminology Criteria for Adverse Events), relationship to IMP, and dose at the time of onset.

The frequency (or incidence) of abuse potential will be summarized by treatment group. Abuse potential will be assessed through the active monitoring of AEs related to potential abuse and AEs involving medication handling irregularities.

Other safety endpoints will be summarized with descriptive statistics by treatment group, including suicidality monitored during the trial using C-SSRS and withdrawal symptoms using the PWC.

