1.4. Treatment Period

Participants will initiate outpatient dosing beginning on Day 1 (the day after the Baseline Visit). During the two-week Titration Period, the participant's dose will be increased in a blinded fashion up to the randomized dose level (darigabat 25 mg BID or placebo BID). In the darigabat 25 mg BID group, darigabat will be administered as 5 mg BID for 1 week followed by 12.5 mg BID for another week during the Titration Period, and then 25 mg BID during the 1two-week Maintenance Treatment Period.

The dosing schedule is shown in [Table 1](#).

Table 1: Dosing Schedule

Blinded Treatment Assignment	Titration Period		Begin Target Dose
	Day 1-7	Day 8-14	Day 15
Darigabat 25 mg BID	5 mg BID	12.5 mg BID	25 mg BID
Placebo	Matching Placebo	Matching Placebo	Matching Placebo

Abbreviation: BID=twice daily.

Participants will continue to record all requested information in the eDiary for each day during both the two-week Titration and 1two-week Maintenance Treatment Periods.

Follow-up telephone contacts will be performed within 3 days and 7 days after the last dose of IMP and an in-clinic follow-up visit will be performed approximately 33 days after the last dose of IMP. The Penn Physician Withdrawal Checklist (PWC) ([Rickels et al, 2008](#)).

will be used to monitor withdrawal symptoms approximately 3 days and 7 days after the last dose of IMP. Participants will continue to record all requested information in the eDiary for each day up to 7 days after the last dose of IMP. Participants should not begin taking their standard-of-care treatment for up to 7 days after the last dose of IMP, if possible.

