3.2.1.2. Treatment-Emergent Adverse Event (TEAE)

Any event reported on the eCRF that occurs on or after the initiation of IMP and through the follow-up contact (i.e., date of Visit 9) is considered treatment-emergent. Additionally, it is an Adverse Event which was reported to have started on Day 1 without an associated onset time is assumed to be treatment emergent.

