4.2. Analysis Periods

The start and ends dates of each analysis period (following the study design) are used for the classification of efficacy data and will be assigned sequentially according to the study day of the event.

Table 4: Definition of Analysis Periods for Efficacy Data

Analysis Period	Duration	Start Day	End Day
Baseline Period	~2 Weeks	The greater of: Study Day -14 or Informed consent	Study Day, -1
Titration Period	~2 Weeks	Study Day, 1	The lesser of: Day 15 minus 1 or **Early termination (minus 1) or End of Treatment

Analysis Period	Duration	Start Day	End Day
Maintenance Period	~12 Weeks	Day 15	The lesser of: Day 98 (Visit 6) or Early Termination (if > Day 15)

** If a participant experiences early termination from the study and continues to Maintenance Period, end dates will be bound by early termination minus 1, while the start of Maintenance Period will begin on the date of early termination.

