6. CHANGES IN THE PLANNED ANALYSES

Analysis methods described here reflect revisions to strategic focus and scope and will supersede those described in the protocol. In addition to changes corresponding to protocol amendments, the analysis plan differs from the statistical analysis section of the protocol as described below:

- As a result of early closure of enrollment and early treatment discontinuation of ongoing participants, planned sample size will not be achieved and proportion of participants with treatment discontinuation will be increased. The resulting sample size will have insufficient power for hypothesis tests and thus, efficacy analysis will be exploratory.
 - The following changes were made to the protocol-specified statistical analysis to reflect the strategic shift to an exploratory evaluation of efficacy
 - Multiplicity adjustments were removed
 - Most sensitivity analyses were removed
 - Supportive analyses involving panic attack-related endpoints were added using an expanded FAS population including all participants regardless of eDiary version used
- Description of handling of ICEs was expanded and revised for the primary and key secondary endpoints:
 - Additional detail was provided for different types of ICEs (eg, administration of rescue medication and treatment discontinuation)
 - Composite strategy was replaced with treatment policy and while on treatment strategies for handling ICEs for analysis of primary and key secondary endpoints
- Added description of missing diary data handling:
 - For the primary efficacy outcome (proportion of participants free of panic attacks), outcome for participants who did not report a panic attack and had <12/14 days of completed eDiary was set to missing, unless otherwise indicated
 - For key secondary efficacy outcome (change from baseline in the frequency of panic attacks), outcome for participants with <7/14 days of completed eDiary was set to missing
- The SAP replaced the SAS® procedure GLIMMIX (specified in protocol) with GENMOD to fit binomial repeated measures model to estimate the proportion of participants that were free of panic attack and the treatment difference. Although both procedures can fit binomial repeated measures model, model-fitting is more efficient with the GENMOD procedure.

Should any deviations from the analyses pre-specified in the authorized statistical analysis plan arise, such deviations will be documented in the final clinical study report.

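### SAP 5.17.1 drops the protocol's adverse-event summary by dose at onset without saying so, and its titration/maintenance split has no place for events after the last dose

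*SAP*

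**What the plan says.** Protocol 9.3.5, like the synopsis, plans TEAE summaries by severity, "relationship to IMP, and dose at the time of onset".

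SAP 5.17.1 keeps summaries by preferred term, system organ class and severity, and separate tables for serious, related, special-interest and discontinuation events. On timing of onset it offers one item: "Presentations of AEs by onset titration versus maintenance period will be prepared". Dose at onset does not appear.

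Three other parts of the SAP bear on that item:

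- Section 1.4 gives two doses inside titration: "darigabat will be administered as 5 mg BID for 1 week followed by 12.5 mg BID for another week during the Titration Period". The dose is then 25 mg BID from Day 15.
- Section 3.2.1.2 sets the TEAE window. An event that "occurs on or after the initiation of IMP and through the follow-up contact (i.e., date of Visit 9) is considered treatment-emergent". Section 1.4 places the in-clinic follow-up visit about 33 days after the last dose.
- Section 4.2, Table 4, is the only definition of titration and maintenance by day. Its title and lead-in confine it to efficacy data. Maintenance there starts at Day 15 and ends at the earlier of Day 98 or early termination, the latter applying only if after Day 15.

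SAP Section 6 states that "the analysis plan differs from the statistical analysis section of the protocol as described below". The list that follows covers multiplicity, sensitivity analyses, intercurrent events, diary data and the modelling procedure. It contains no safety item.

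**The concern.** Safety and tolerability is the trial's secondary objective, and withdrawal symptoms are a named endpoint under it. Two questions depend on when an event began relative to dosing.

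The first is which titration step an event belongs to. Protocol 4.3.1 says titration may mitigate central nervous system events, and Protocol 2.2.2.2 reports a severe panic attack on Day 4, in the first week of titration, in an earlier trial. A single titration level cannot separate the two steps.

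The second is whether an event began on drug or after stopping. Darigabat binds the benzodiazepine site (Protocol 2.2.2). The withdrawal checklist is scheduled only to about 7 days after the last dose, while TEAEs are collected to about 33 days. Adverse-event onset is therefore the main evidence on later withdrawal effects, yet the onset table has no level for it. The SAP does make this distinction elsewhere: Sections 3.2.6 and 5.17.2 give medications a post-last-dose class.

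Because the SAP states that it supersedes the protocol's analyses, the dose-at-onset summary would not be produced by default, and a reader of Section 6 would not learn that it had gone.

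**Working it through.** **Inputs.** Dosing schedule: 5 mg BID on Days 1–7, 12.5 mg BID on Days 8–14, 25 mg BID from Day 15 (SAP Table 1). Last treatment visit Day 98 and last follow-up visit Day 131 (SAP 4.1.18). Follow-up about 33 days after the last dose (SAP 1.4). TEAE window from first dose to Visit 9 (SAP 3.2.1.2).

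**Step 1: the plan's own figure.** 131 − 98 = 33 days, matching the stated follow-up.

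**Step 2: a completer's TEAE window by dose at onset.** 7 days at 5 mg BID + 7 at 12.5 mg BID + 84 at 25 mg BID (98 − 14) + 33 off drug = 131 days. Off-drug share: 33/131 = 25.2%. The protocol's summary, with a post-last-dose level, would have four cells; the SAP split has two.

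**Step 3: where the 33 off-drug days go.** The SAP does not say, so both available readings are worked.

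- *Reading A: maintenance means every onset from Day 15 to Visit 9.* Maintenance has 131 − 14 = 117 days, of which 33/117 = 28.2% are off drug.
- *Reading B: the Table 4 efficacy bounds are borrowed.* Maintenance ends at Day 98. Days 99–131, all 33 off-drug days, fall in neither period, and events starting then are missing from the onset table.

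**Step 4: earlier stops.** The documents give no distribution of stopping days, so the days below are illustrative, each with 33 days of follow-up. For a last dose on Day L (L ≥ 14), the off-drug share is 33/(L + 33) of the TEAE window and, under Reading A, 33/(L + 33 − 14) of maintenance.

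| Last dose (assumed) | Share of TEAE window | Share of maintenance, Reading A |
|---|---|---|
| Day 98 | 33/131 = 25.2% | 33/117 = 28.2% |
| Day 70 | 33/103 = 32.0% | 33/89 = 37.1% |
| Day 42 | 33/75 = 44.0% | 33/61 = 54.1% |
| Day 28 | 33/61 = 54.1% | 33/47 = 70.2% |

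Under Reading B, 33 days stay unassigned in every row. SAP Section 6 expects more treatment discontinuation because of early closure, which moves participants down the table.

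**The case against.** The strongest reply is that little is lost. The main TEAE tables count events through last follow-up by treatment group, all adverse events are listed, and withdrawal is assessed separately with the checklist. Protocol 6.5 says "No dose modifications are permitted during the trial", so while a participant is on drug the study day identifies the planned dose, and an on-drug maintenance onset corresponds to 25 mg BID. Separating two one-week steps in a trial closed early gives small cells. The shares above are of days, not of events. All of this stands and limits the point to one descriptive presentation. It does not supply the missing off-drug level or explain the unlisted change.

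A reader might go further and infer that the SAP attributes events to doses the participant was not taking. The text does not support that. SAP 5.17.1 presents periods, not doses. Pooling 5 and 12.5 mg BID loses resolution but assigns no wrong dose. The documents treat follow-up as separate from a 12-week maintenance period ending at Day 98, so carrying maintenance on to Visit 9 is a possible reading but not a stated rule.

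The Table 4 footnote invites the same inference for people who stop in titration, saying of an early terminator "while the start of Maintenance Period will begin on the date of early termination". But it is conditional on the participant continuing to maintenance, its wording is unclear, and it belongs to a table for efficacy data. It shows why adverse-event periods need their own definition; it does not show how adverse events will be classified.

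**Conclusion.** The point holds as an undeclared omission and an undefined classification. The protocol's dose-at-onset summary is absent from the SAP and from its list of changes. The replacement is implied by omission, since the SAP never states it. The remaining split merges the two titration doses and leaves about 33 off-drug days per participant without a level.

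For a completer that is 25% of the TEAE window. Those days make up 28% of maintenance under one reading and are outside the table under the other. Either result is less informative than the summary the protocol promised. The completer figures assume a last dose on Day 98 and Visit 9 on Day 131. The figures for earlier stops rest on assumed stopping days. None of them predicts how many events will be affected.

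**What to change.** In SAP 5.17.1, restore the protocol summary. Classify each TEAE from actual dosing dates as onset during 5 mg BID, 12.5 mg BID, 25 mg BID (or the matching placebo period), or after the last dose. Show the number of participants at risk in each category.

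If the titration/maintenance presentation is kept as well, add a post-last-dose column and state that the Table 4 efficacy periods do not govern adverse events. List any departure that remains in Section 6.

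One footnote is worth adding. Under SAP 4.1.19, an onset with a missing day in the same month as IMP is set to Day 1, so it would land in the 5 mg BID category. Such events should be flagged.

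The cost is SAP wording and one reprogrammed table. Daily dosing, the last-dose date and event onset dates are already collected (SAP 4.1.8, 4.1.17 and 5.17.1). The downside is smaller cells per category, which the numbers at risk will make visible.

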5.17.2. Medications and Non-Drug Therapy/Procedures

Prior medications, concomitant medications, and medications taken post last dose of IMP will be coded using the World Health Organization (WHO) drug dictionary (WHODrug) (Version: March 2024). Prior medications and concomitant medications will be summarized by treatment group, frequency of drug classification, and generic drug name. All medications will be presented in a data listing.

Non-drug therapy/procedures will be coded using MedDRA Versions 27.0 and 27.1.

Concomitant non-drug therapy/procedures will be summarized by treatment group, frequency of system organ class and preferred term. All non-drug therapy/procedures will be presented in a data listing.

5.17.3. Clinical Laboratory Assessments

Descriptive summaries of selective (quantitative) clinical laboratory results and change from baseline will be presented by study visit.

Additionally, for hematology, blood chemistry, coagulation, and urinalysis parameters, toxicity grade will be determined for laboratory tests with toxicity grade specified in [Section 9.5](#). Shifts from baseline to greatest (worst) post-baseline laboratory grade will be presented. For parameters not graded as described above, laboratory values outside the normal range for each systematically collected hematology, blood chemistry, and urinalysis parameters defined in Protocol Section 10.2 will be identified using shift tables. Each subject's hematology, blood chemistry, and quantitative urinalysis values will be flagged as "low" (below the lower limit of normal/LLN), "normal" (within the normal range), or "high" (above the upper limit of normal/ULN) relative to the normal ranges of the central laboratory. Each subject's qualitative urinalysis values will be flagged as "normal" or "abnormal". Shifts from baseline to high/normal/low status for the hematology, blood chemistry, and urinalysis parameters will be presented to for the maximum post-baseline value and the minimum post-baseline value for each laboratory test. Shifts from baseline to normal/abnormal status for urinalysis parameters will be presented to the maximum post-baseline value and the minimum post-baseline value for each laboratory test.

The number and percentage of participants who have post-baseline elevations in liver transaminase (alanine aminotransferase [ALT] or aspartate aminotransferase [AST]) or bilirubin abnormalities in relation to fold above the upper limit of normal will be summarized according to the Food and Drug Administration's Premarketing Clinical Evaluation on Drug-Induced Liver Injury Guidance for Industry ([FDA, 2009](#)). Abnormal hepatic laboratory values will be categorized and evaluated for any occurrence among all post-baseline assessments (where "and" in the bulleted list below indicates elevations occurring at the same visit). Within each laboratory parameter grouping, a participant may be counted once per elevation criteria using the worst-case result. That is, a participant with a worst-case ALT elevation $>5 \times$ the ULN would be counted once in the ALT $> 3 \times$ ULN category and once in the ALT $> 5 \times$ ULN category, regardless of how many ALT elevations the participant had that met the $> 5 \times$ ULN and $> 3 \times$ ULN elevation criteria.

- ALT and/or AST $> 3 \times$ ULN and total bilirubin > 1.5 or $2 \times$ ULN
- AST $> 3, 5, 10, 20 \times$ ULN
- ALT $> 3, 5, 10, 20 \times$ ULN
- Total bilirubin $> 1.5, 2 \times$ ULN
- Alkaline phosphatase (ALP) $> 1.5 \times$ ULN

In addition, a Hy's law plot, a shift plot showing liver safety panel tests over time (baseline vs. post-baseline), and distribution plots of ALT, AST, ALP, and bilirubin over time will be produced using the format recommended by the Food and Drug Administration (FDA)/Industry/Academia Safety Graphics working group (<https://www.ctspedia.org/do/view/CTSpedia/StatGraphHome>). The plots to be included are the scatter plot of maximum transaminase versus maximum bilirubin, the liver test safety panel over time, and the distribution of ALT by time. The distribution plots for AST, ALP, and bilirubin will use the same format as used for ALT.

5.17.4. Vital Signs

Vital signs and corresponding changes from baseline will be summarized by position (if applicable), visit, and timepoint using descriptive statistics. Vital signs results, including orthostatic changes, will be listed.

Out of range vital signs occurring post study baseline will be summarized. For supine blood pressure and heart rate, only averages of duplicates will be used. If an average is not available, the single reading will be used for summary.

The following out-of-range criteria will be summarized for post study baseline assessments:

- Systolic Blood Pressure (Supine)
 - ≤ 90 mmHg
 - ≥ 140 mmHg
- Orthostatic Change in Systolic Blood Pressure
 - ≥ 20 mmHg decrease upon standing compared with supine position
- Diastolic Blood Pressure (Supine)
 - ≤ 60 mmHg
 - ≥ 90 mmHg
- Orthostatic Change in Diastolic Blood Pressure
 - ≥ 10 mmHg decrease upon standing compared with supine position
- Heart Rate
 - < 60 bpm
 - > 100 bpm
- Respiratory Rate
 - < 12 breaths/min
 - > 20 breaths/min
- Temperature
 - $< 36^{\circ}$ C
 - $> 38^{\circ}$ C
- Body weight
 - $\geq 7\%$ increase
 - $\geq 7\%$ decrease

5.17.5. 12-Lead Electrocardiograms

Single or triplicate 12-lead electrocardiograms (ECGs) will be obtained during the trial. Any values taken in triplicate will be averaged for analysis. ECGs and corresponding changes from baseline will be summarized by treatment group and visit using descriptive statistics.

The number and percentage of participants who experience any post-baseline occurrence of potentially clinically significant QTcF will be summarized by treatment group. These presentations will include QTcF values > 450 to ≤ 480 , > 480 to ≤ 500 , and > 500 msec; or changes of > 30 to ≤ 60 or > 60 msec.

Additionally, a distribution plot of QTcF over time may be produced using the format recommended by the FDA/Industry/Academia Safety Graphics working group (<https://www.ctspedia.org/do/view/CTSpedia/StatGraphHome>). The graph format to be used is the same graph provided for the distribution of ALT by time and treatment.

5.17.6. Physical and Neurological Examinations

Physical and neurological examination data will be listed.

5.17.7. Missing Visits and Assessments due to COVID-19

The number and proportion of missing visits and key assessments due to COVID-19 control measures and the frequency of remote assessments performed due to COVID-19 restrictions will be tabulated by treatment, visit, and assessment as well as the overall number and proportion of participants with any such missing visits, assessments, or remote visits in each treatment group if required

